#### 5.3.2.4 Hospital & Provider Characteristics

- Hospital arthroplasty procedure volume for the specific arthroplasty type during BASELINE
- Surgeon arthroplasty procedure volume for the specific arthroplasty type during BASELINE
- Hospital: Bed size
- Hospital: Teaching status
- Hospital: Rural vs urban

#### 5.3.3 Outcome(s) or Dependent Variable(s)

#### 5.3.3.1 Outcomes for Primary Objective(s) – Primary Endpoint

- Heart failure cases diagnosed in the first 30-days post implantation (index date) will be excluded to prevent including cases of iatrogenic fluid overload due to the surgical procedure
- > 2 recorded acute heart failure-related diagnosis codes

ICD-9-CM Code	Code Description
428.0	Congestive heart failure, unspecified
428.1	Left heart failure
428.20	Systolic heart failure, unspecified
428.21	Systolic heart failure, acute
428.23	Systolic heart failure, acute on chronic
428.30	Diastolic heart failure, unspecified
428.31	Diastolic heart failure, acute
428.33	Diastolic heart failure, acute on chronic

428.40	Combine systolic and diastolic heart failure, unspecified
428.41	Combine systolic and diastolic heart failure, acute
428.43	Combine systolic and diastolic heart failure, acute on chronic
428.9	Heart failure, unspecified

#### ICD-10-CM Code

D-10-CIVI COUC	coue Description	
150.20	Unspecified systolic (congestive) heart failure	
150.21	Acute systolic (congestive) heart failure	
150.23	Acute on chronic systolic (congestive) heart failure	
150.30	Unspecified diastolic (congestive) heart failure	
150.31	Acute diastolic (congestive) heart failure	
150.33	Acute on chronic diastolic (congestive) heart failure	
150.81	Right heart failure	
150.83	High output heart failure	
150.89	Other heart failure	
150.84	End stage heart failure	
150.82	Biventricular heart failure	
150.9	Heart failure, unspecified	
150.4	Combined systolic (congestive) and diastolic (congestive) heart failure	
111.0	Hypertensive heart disease with heart failure	
113.2	Hypertensive heart and chronic kidney disease with heart failure and with	
	stage 5 chronic kidney disease, or end stage renal disease	
113.0	Hypertensive heart and chronic kidney disease with heart failure and stage 1 through stage 4 chronic kidney disease, or unspecified chronic kidney disease	

Code Description

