#### 5.3.3.2 Outcomes for Primary Objective(s) – Secondary Endpoint

- Heart failure cases diagnosed in the first 30-days post implantation (index date) will be excluded to prevent including cases of iatrogenic fluid overload due to the surgical procedure
- > 2 recorded acute or chronic heart failure-related diagnosis codes

ICD-9-CM Code	Code Description		
428.0	Congestive heart failure, unspecified		
428.1	Left heart failure		
428.20	Systolic heart failure, unspecified		
428.21	Systolic heart failure, acute		
428.22	Systolic heart failure, chronic		
428.23	Systolic heart failure, acute on chronic		
428.30	Diastolic heart failure, unspecified		
428.31	Diastolic heart failure, acute		
428.32	Diastolic heart failure, chronic		
428.33	Diastolic heart failure, acute on chronic		
428.40	Combine systolic and diastolic heart failure, unspecified		
428.41	Combine systolic and diastolic heart failure, acute		
428.42	Combine systolic and diastolic heart failure, chronic		
428.43	Combine systolic and diastolic heart failure, acute on chronic		
428.9	Heart failure, unspecified		

ICD-10-CM Code	Code Description		
150.20	Unspecified systolic (congestive) heart failure		
150.21	Acute systolic (congestive) heart failure		
150.22	Chronic systolic (congestive) heart failure		
150.23	Acute on chronic systolic (congestive) heart failure		
150.30	Unspecified diastolic (congestive) heart failure		
150.31	Acute diastolic (congestive) heart failure		
150.32	Chronic diastolic (congestive) heart failure		
150.33	Acute on chronic diastolic (congestive) heart failure		
150.81	Right heart failure		
150.83	High output heart failure		
150.89	Other heart failure		
150.84	End stage heart failure		
150.82	Biventricular heart failure		
150.9	Heart failure, unspecified		
150.4	Combined systolic (congestive) and diastolic (congestive) heart failure		
111.0	Hypertensive heart disease with heart failure		
113.2	Hypertensive heart and chronic kidney disease with heart failure and with		
	stage 5 chronic kidney disease, or end stage renal disease		
113.0	Hypertensive heart and chronic kidney disease with heart failure and stage 1 through stage 4 chronic kidney disease, or unspecified chronic kidney disease		

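### The primary endpoint is labelled acute heart failure, but most of its codes state no acuity, and its ICD-9 and ICD-10 lists follow different rules, so the outcome definition changes with coding era

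*Protocol*

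**What the plan says.** Section 5.3.3.1 requires "> 2 recorded acute heart failure-related diagnosis codes" for the primary endpoint. Section 5.3.3.2 requires "> 2 recorded acute or chronic heart failure-related diagnosis codes" for the secondary. Each gives one ICD-9-CM and one ICD-10-CM list. (The extracted text prints I50.x as 150.x, and I11/I13 as 111/113. This is a reading artefact and is ignored here.)

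- The primary ICD-9 list contains only 428.x codes. It includes "Congestive heart failure, unspecified" (428.0) and "Left heart failure" (428.1). For combined failure it keeps 428.40, 428.41 and 428.43, the last being "Combine systolic and diastolic heart failure, acute on chronic". It leaves out 428.42, "Combine systolic and diastolic heart failure, chronic", which appears only in the secondary list.
- The primary ICD-10 list splits systolic (I50.2x) and diastolic (I50.3x) failure by acuity and drops the chronic codes. It enters I50.4, "Combined systolic (congestive) and diastolic (congestive) heart failure", as one undivided category, and the secondary list carries the same entry. It also includes I11.0, "Hypertensive heart disease with heart failure", and I13.0 and I13.2.

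Section 5.2 sets indexing from October 2005 to December 2017 and ends the study period in June 2018. Section 5.4.3 plans Cox regression with either propensity score matching or stratification. Calendar year and year of index date are listed variables (sections 5.3.2.1 and 5.3.2.2), but no rule fixes their use in the primary model. Section 5.4.4 lists stratification by coding system among the sensitivity analyses. The synopsis describes the endpoint without the word acute.

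**The concern.** Two separate defects affect the primary endpoint of both co-primary comparisons.

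First, the label and the list disagree. A report that presents this endpoint as acute heart failure would misdescribe what was counted.

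Second, the rule that makes the primary list differ from the secondary one, leaving out codes stated as chronic, is applied to combined failure in ICD-9 but not in ICD-10. Left-sided and hypertensive entries each appear in one system only. A patient followed across the coding change is therefore assessed under two definitions, and whether the same condition counts as an event depends on the date of the claim. That is an internal inconsistency in the pre-specified outcome, whatever its effect on the hazard ratio. If the arms also contribute different shares of person-time under ICD-10, part of the estimated hazard ratio would reflect coding and not heart failure.

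**Working it through.** **Step 1: count the entries** (sections 5.3.3.1 and 5.3.3.2).

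| | Primary | State acute or acute on chronic | Secondary | Added in secondary |
|---|---|---|---|---|
| ICD-9 | 12 | 6 (428.21, .23, .31, .33, .41, .43) | 15 | 3 (428.22, .32, .42) |
| ICD-10 | 16 | 4 (I50.21, .23, .31, .33) | 18 | 2 (I50.22, I50.32) |

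Together, 6 + 4 = 10 of 12 + 16 = 28 primary entries state acuity and 18 do not. Those 18 include unspecified, end-stage, right, biventricular, high-output and hypertensive entries.

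**Step 2: set the two systems side by side in the primary list.**

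| Condition | ICD-9 | ICD-10 |
|---|---|---|
| Chronic systolic or diastolic | left out | left out |
| Chronic combined | left out (428.42) | not separated (I50.4 entered whole) |
| Hypertensive heart disease with failure | no such entry | I11.0, I13.0, I13.2 |
| Left heart failure | 428.1 | no left-sided entry |

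The I50.4 entry is inconsistent on either reading. If it stands for every code beneath it, chronic combined failure is an event in ICD-10 and not in ICD-9. If the string is matched exactly, claims carrying a more detailed combined code are missed in ICD-10 while 428.40, 428.41 and 428.43 count in ICD-9. The protocol does not say which applies.

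**Step 3: what a between-arm imbalance could do.** The protocol has no figure to reproduce here: it gives no index-date distribution by arm, no switch date and no event rates by code list. As a crude rate-ratio approximation,

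factor = (1 + f1(k − 1)) / (1 + f0(k − 1)),

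where f1 and f0 are the two arms' shares of person-time under ICD-10 and k is the event rate under the ICD-10 list divided by that under the ICD-9 list.

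Assumptions: one arm is indexed evenly from October 2005 to the end of 2012, the other evenly to the end of 2017. Person-time runs from day 30 to mid-2018, with an exit hazard of 0.05 to 0.20 per year. The switch falls between late 2014 and late 2016, and k is 1.10 to 1.50. The ICD-10 share is then 9 to 37% in the early arm and 20 to 48% in the other.

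- Largest shift: f1 = 0.243, f0 = 0.409, k = 1.50 gives 1.1215/1.2045 = 0.93.
- Middle case: f1 = 0.223, f0 = 0.338, k = 1.25 gives 1.0558/1.0845 = 0.97.
- Smallest shift: f1 = 0.162, f0 = 0.236, k = 1.10 gives 1.0162/1.0236 = 0.99.
- Narrower ICD-10 list: middle-case shares with k = 0.80 give 0.9554/0.9324 = 1.02, so the direction reverses.
- Equal shares (f1 = f0) or equivalent lists (k = 1) give exactly 1.00.

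**Step 4: scale.** Section 5.3.4 gives 18,521 MoM patients and no alpha, power or target effect. Assume 1:1 matching and apply to both arms the metal-on-polyethylene incidences from the earlier Medicare study cited in section 3 (7.06% at three years, 9.49% at four). Events = 2 × 18,521 × 0.0706 = 2,615, or × 0.0949 = 3,515. The 95% confidence limits then lie a factor exp(1.96 × 2/√events) = 1.08 or 1.07 from the estimate. The hazard ratio detectable with 80% power at two-sided 5% is exp(2.80 × 2/√events) = 1.12 or 1.10. A 1 to 7% shift is therefore at most about the half-width of the confidence interval.

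**The case against.** The best defence has four parts.

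*The coding change is already handled.* Section 5.4.4 stratifies by coding system and names heart failure ascertainment as a reason, and index year is a listed variable. This has weight. Balancing index year with similar follow-up would bring the between-arm factor close to 1.00, and the choice of propensity covariates is commonly left to a statistical analysis plan. But stratification as a sensitivity analysis leaves the primary hazard ratio on the mixed definition, and neither measure repairs the label or the I50.4 entry.

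*The lists are provisional.* Section 5.3 promises final code lists in the study report. That comes after the analysis. The lists printed now are the pre-specified ones, and they conflict with each other.

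*The label is only a name.* The objectives and synopsis concern heart failure generally, and patients with acute or chronic heart failure at baseline are excluded, so keeping unspecified codes to capture incident disease is defensible. This stands, and it argues for renaming the endpoint. A reader might infer that the primary list must be cut to strictly acute codes. The documents do not require that, and it would drop 428.0 and 428.9 at an unknown cost in events.

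*No bias against either arm is shown.* This also stands. A reader might infer that MoM use fell over time, that ICD-10 is the broader list, and that the MoM hazard ratio is therefore pulled down. The protocol gives no calendar distribution by arm. The missing left-sided entry makes ICD-10 narrower, and so would exact matching of I50.4. The hypertensive codes add events only in patients who do not otherwise meet the definition, a share the protocol does not give.

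**Conclusion.** The point holds as an error in the definition of the primary endpoint. From the text alone, the acute label does not describe the list, the exclusion of chronic codes is applied to combined failure in ICD-9 but not in ICD-10, and left-sided and hypertensive entries each appear in one system only. With both lists in use up to June 2018, the outcome definition depends on coding era.

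The effect on the hazard ratio is a conditional risk of unknown sign. It needs both non-equivalent capture and unequal ICD-10 person-time between arms. Under the stated assumptions it is about 1 to 7%; with balanced person-time it is nil.

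Two stronger readings go too far. One is that the artefact is as large as the effect sought: the protocol states no target effect, and the detectable ratio of 1.10 to 1.12 rests on assumed matching and borrowed incidences. The other is that the secondary endpoint adds almost nothing because it adds only five codes: codes are not events, and no code frequencies are given.

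**What to change.** 1. In the primary ICD-10 list, replace I50.4 with its unspecified, acute and acute-on-chronic subcodes, following the pattern used for I50.2 and I50.3. Keep the chronic subcode for the secondary list only.
2. Map left-sided and hypertensive heart failure across the two systems so that both include, or both exclude, the same conditions.
3. Rename the primary endpoint as heart failure excluding codes stated as chronic, noting that acute-on-chronic codes are retained, and align the synopsis. A strictly acute list should be a sensitivity analysis at most, since it would yield fewer events.
4. Fix index calendar year as a matching or stratification factor in the primary Cox analysis, so that compared patients cross the coding change at similar follow-up times. Keep the section 5.4.4 stratification as a check.

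The cost is a few code-list edits, using a variable already planned, and possibly a few unmatched patients if matching on index year is chosen. The edits should be made before the data specification is finalised and the analytic file is built.

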#### 5.3.3.2 Outcomes for Primary Objective(s) – Secondary Endpoint

- Heart failure cases diagnosed in the first 30-days post implantation (index date) will be excluded to prevent including cases of iatrogenic fluid overload due to the surgical procedure
- > 2 recorded acute or chronic heart failure-related diagnosis codes

ICD-9-CM Code	Code Description		
428.0	Congestive heart failure, unspecified		
428.1	Left heart failure		
428.20	Systolic heart failure, unspecified		
428.21	Systolic heart failure, acute		
428.22	Systolic heart failure, chronic		
428.23	Systolic heart failure, acute on chronic		
428.30	Diastolic heart failure, unspecified		
428.31	Diastolic heart failure, acute		
428.32	Diastolic heart failure, chronic		
428.33	Diastolic heart failure, acute on chronic		
428.40	Combine systolic and diastolic heart failure, unspecified		
428.41	Combine systolic and diastolic heart failure, acute		
428.42	Combine systolic and diastolic heart failure, chronic		
428.43	Combine systolic and diastolic heart failure, acute on chronic		
428.9	Heart failure, unspecified		

ICD-10-CM Code	Code Description		
150.20	Unspecified systolic (congestive) heart failure		
150.21	Acute systolic (congestive) heart failure		
150.22	Chronic systolic (congestive) heart failure		
150.23	Acute on chronic systolic (congestive) heart failure		
150.30	Unspecified diastolic (congestive) heart failure		
150.31	Acute diastolic (congestive) heart failure		
150.32	Chronic diastolic (congestive) heart failure		
150.33	Acute on chronic diastolic (congestive) heart failure		
150.81	Right heart failure		
150.83	High output heart failure		
150.89	Other heart failure		
150.84	End stage heart failure		
150.82	Biventricular heart failure		
150.9	Heart failure, unspecified		
150.4	Combined systolic (congestive) and diastolic (congestive) heart failure		
111.0	Hypertensive heart disease with heart failure		
113.2	Hypertensive heart and chronic kidney disease with heart failure and with		
	stage 5 chronic kidney disease, or end stage renal disease		
113.0	Hypertensive heart and chronic kidney disease with heart failure and stage 1 through stage 4 chronic kidney disease, or unspecified chronic kidney disease		

#### 5.3.3.3 Outcomes for Secondary Objective(s)

• Variables noted in sections above

#### 5.3.3.4 Other Variables

N/A

#### 5.3.4 Sample Size and Study Power

A previous analysis of the Medicare SAF database identified 18,521 patients with MoM hip implants between 2005 and 2015.

## 5.4 Data Analysis(es)

The goals of these analyses are to: 1) determine the characteristics of patients implanted with MoM and non-MOM hip implants and OA patients with arthroplasty, and 2) evaluate the risk of heart failure among patients with MoM implants compared to non-MOM implants or OA without arthroplasty.

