## 4. Research Questions and Objectives

### 4.1 Research Question

Are patients with Metal-on-Metal arthroplasties of the hip at an increased risk of developing heart failure?

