## 4.2 Research Objectives

#### 4.2.1 Primary objective(s):

- To estimate the incidence and evaluate the risk of heart failure among patients undergoing MoM arthroplasties of the hip compared with those with alternative types of arthroplasties (non-MoM)
- To estimate the incidence and evaluate the risk of heart failure among patients undergoing MoM arthroplasties of the hip compared with an age and gender similar Osteoarthritis cohort without arthroplasty

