#### 5.2.1 Inclusion criteria

THA patients must meet ALL the following criteria to be included in study:

- Elective, primary THA performed in inpatient setting (first occurrence is the index date)
- >65 years
- Enrolled in the data source for at least 365 days prior to index procedure (baseline period)

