#### 5.4.2 Incidence Rate of Heart Failure

The number of new cases of heart failure will be determined. Person-time for each patient will be calculated from 30 days after index date to the first diagnosis code of heart failure (at-risk time interval). The incidence rate of heart failure will be determined for each study cohort as the number of new cases of heart failure during the observation period divided by the total person-time of observation among the patients at risk. The results will be reported as a point estimate (in cases/1000 person-years) and

95% CI. Confidence intervals will be based on asymptotic theory assuming the outcome follows a Poisson distribution.

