#### 5.4.3 Risk of Heart Failure Associated with MoM Implants

Cox proportional hazards regression will be performed to determine HRs of heart failure with 95% Cis in MoM implants versus non-MOM implant and MoM implants versus RA patients without arthroplasty. Propensity score matching or stratification will be used to control for confounding.

If a significantly higher risk of heart failure is identified for patients with MoM implants, Cox proportional hazards regression will be conducted to determine risk factors for a diagnosis of heart failure.

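### The second co-primary (MoM hips vs OA without arthroplasty) mixes the bearing with selection for, and effects of, hip surgery, and no adjusted non-MoM vs OA contrast is planned to show how large the surgical part is

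*Protocol*

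**What the plan says.** Section 4.1 asks: "Are patients with Metal-on-Metal arthroplasties of the hip at an increased risk of developing heart failure". Section 4.2.1 answers with two co-primary objectives. One is MoM hips "compared with those with alternative types of arthroplasties (non-MoM"; the other is MoM hips "compared with an age and gender similar Osteoarthritis cohort without arthroplasty". Section 5.3.1 lists three exposure groups.

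The hip cohorts enter through "Elective, primary THA performed in inpatient setting (first occurrence is the index date" (5.2.1). The OA cohort enters through recorded OA diagnosis codes, with no operation required.

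Section 5.4 gives the risk goal of the analysis as to "evaluate the risk of heart failure among patients with MoM implants compared to non-MOM implants or OA without arthroplasty". Section 5.4.3 plans two hazard ratios: "MoM implants versus non-MOM implant and MoM implants versus RA patients without arthroplasty". (It writes RA where the objectives say OA. That is a separate wording error to reconcile.) On adjustment it says: "Propensity score matching or stratification will be used to control for confounding". It then makes risk-factor modelling conditional on a significantly raised risk in MoM patients, without saying against which comparator.

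Section 5.4.2 adds: "The incidence rate of heart failure will be determined for each study cohort". These rates are unadjusted.

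**The concern.** The MoM vs OA contrast bundles three things: being judged fit for elective inpatient surgery, any effect of hip replacement itself, and the metal-on-metal bearing. The non-MoM hips share the first two and lack the third, so they are the natural control for this contrast. The plan uses them only against MoM.

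The MoM vs OA result has co-primary rank and no stated rule for reading it. A ratio near or below 1 could be taken as reassurance about metal when it reflects healthier patients being chosen for surgery. A ratio above 1 could come from arthroplasty in general, and as 5.4.3 is worded it could still start the risk-factor modelling. If the two co-primaries disagree, no planned adjusted analysis shows why.

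**Working it through.** **1. Contrasts planned**

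| Protocol section | MoM vs non-MoM | MoM vs no arthroplasty | Non-MoM vs OA |
|---|---|---|---|
| 4.2.1 objectives | yes | yes | no |
| 5.4 goals | yes | yes | no |
| 5.4.2 incidence | crude rate | crude rate | crude rates only |
| 5.4.3 Cox models | yes | yes | no |
| 5.4.4 sensitivity | changes outcome, coding era or non-MoM group | – | no |

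Section 5.4.1 tests baseline characteristics between cohorts, not heart failure.

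**2. Whether the planned adjustment can separate the parts**

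Length of stay and MS-DRG (5.3.2.2) and surgeon volume for the arthroplasty type (5.3.2.4) describe a surgical episode that OA patients do not have. These covariates cannot balance MoM against OA. The shared claims comorbidities can adjust for part of fitness for surgery, but section 5.1 limits Part B to institutional outpatient providers, so that record is thin.

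**3. Figures available**

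Section 5.3.4 gives 18,521 MoM patients (2005 to 2015) and no power, alpha or target hazard ratio, so there is no design figure to reproduce. Section 3 cites an earlier Medicare study with heart failure in 6.60% of MoM vs 7.06% of MoP patients at three years, and 8.73% vs 9.49% at four. As a check on those inputs:

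- (0.0660/0.9340)/(0.0706/0.9294) = 0.930, cited as 0.93
- (0.0873/0.9127)/(0.0949/0.9051) = 0.912, cited as 0.91

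**4. Illustration of the mixing**

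Take HR(MoM vs OA) = HR(bearing) × HR(surgery), where HR(surgery) covers selection and any effect of the operation. All values of both factors are assumptions.

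| HR(bearing) | surgery 0.7 | 0.8 | 0.9 | 1.1 |
|---|---|---|---|---|
| 1.0 | 0.70 | 0.80 | 0.90 | 1.10 |
| 1.2 | 0.84 | 0.96 | 1.08 | 1.32 |

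The same observed ratio can arise in different ways: 0.90 = 1.0 × 0.9 = 1.5 × 0.6. The contrast alone does not identify the bearing effect.

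**5. What the sample size does with this**

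Assume 1:1 groups, two-sided 0.05 and N = 18,521 MoM patients with risk r of 6.60% or 8.73%. Schoenfeld's approximation gives

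chance of p<0.05 = Φ(√(d/4) × |ln HR| − 1.96), with events d = N·r·(1 + 1/HR).

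- No bearing effect, surgery 0.9, MoM vs OA shows 0.90: d = 2,580, √645 × 0.1054 − 1.96 = 0.72, chance 76%. At 8.73%, d = 3,413, chance 87%.
- No bearing effect, surgery 1.1, MoM vs OA shows 1.10: d = 2,333, √583.25 × 0.0953 − 1.96 = 0.34, chance 63%. At 8.73%, d = 3,086, chance 75%.
- Bearing 1.2, surgery 0.8, MoM vs OA shows 0.96: taking equal risks, d = 2·N·r = 2,444, √611 × 0.0408 − 1.96 = −0.95, chance 17%. At 8.73%, d = 3,233, chance 21%.
- The same bearing effect in MoM vs non-MoM, HR 1.2: d = 2,241, √560.25 × 0.1823 − 1.96 = 2.36, chance 99%. At 8.73%, d = 2,964, chance above 99%.

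**The case against.** The strongest reply is that the bearing question is already answered by the other co-primary. It compares MoM with non-MoM hips that all entered through elective inpatient THA, and section 3 names that association as the study's purpose. This stands. A reader might infer that a 20% excess from metal would go unseen, or that the study cannot answer its question. The documents do not support that: in the illustration, MoM vs non-MoM detects a ratio of 1.2 with about 99% power. The protocol also never says that MoM vs OA isolates metal, and two comparators for two questions is a legitimate design.

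Second, the ratio of MoM vs OA to non-MoM vs OA targets the same quantity as MoM vs non-MoM, so it adds little about metal. This also stands. Dividing the two planned hazard ratios would likewise give a rough non-MoM vs OA figure (0.96/1.2 = 0.80). But separately matched sets can represent different populations, and the protocol does not plan that step.

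Third, crude rates by cohort already allow a non-MoM vs OA look. That is true, but they cannot calibrate an adjusted hazard ratio.

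Fourth, supportive contrasts may sit in a statistical analysis plan that is not shown. The protocol, however, itself fixes the co-primary contrasts and leaves the comparator in the 5.4.3 trigger open, so the point concerns what this document decides.

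Finally, MoM and non-MoM patients may not have been selected for surgery in the same way, and nothing in the protocol establishes that they were. This limits what the added contrast can show.

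**Conclusion.** The point holds for the second co-primary only. Taken alone, MoM vs OA cannot attribute a difference, or the lack of one, to the bearing, and the plan has no adjusted non-MoM vs OA estimate to show how much of it belongs to surgery. It would go too far to call the contrast uninterpretable: it can describe how MoM patients fare against unoperated OA patients, which is what the objective literally asks.

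The size cannot be derived from the documents. The surgery hazard ratios of 0.7 to 0.9 and 1.1, the 1:1 groups and the multiplicative form are assumptions. The event risks are borrowed from a cited study and may not match this protocol's endpoint or follow-up. Under those assumptions, a surgery component of only 10% in either direction would often reach significance with no bearing effect at all. This is a worthwhile, low-cost improvement, not a defect that defeats the study.

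**What to change.** In sections 5.4 and 5.4.3:

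- Add an adjusted hazard ratio for non-MoM THA vs OA without arthroplasty as a prespecified supportive negative-control contrast. Use the same outcome, 30-day rule, propensity method and Cox model as MoM vs OA, and restrict covariates to those defined in both cohorts.
- State that a MoM vs OA difference is attributed to metal only if MoM vs non-MoM agrees and non-MoM vs OA does not show a similar difference. State also that a null MoM vs OA result is not by itself evidence against a bearing effect.
- Say that the risk-factor modelling is triggered by the MoM vs non-MoM result.
- Treat the ratio of the two OA-based hazard ratios as optional.

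The cost is one more propensity score and Cox run on cohorts already being built, and a more conditional second co-primary claim. The contrast calibrates only so far as MoM and non-MoM patients share the same surgical selection. It also inherits the OA cohort's index date, which 5.2.1 ties to a procedure that cohort does not have; that must be settled separately.
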